**REVISION HISTORY**

Version	Issue Date	Summary of Changes
Draft 1.0	31 Aug 2018	New Document
Draft 2.0	01 Nov 2018	Minor editorial changes resulting for Shire review of version 1.0
Final 1.0	19Jan2019	Finalize

## 1. INTRODUCTION

This is a pilot study to assess the safety and efficacy of alpha1-proteinase inhibitor (A1PI) augmentation therapy in subjects with emphysema/chronic obstructive pulmonary disease (COPD) associated with severe congenital A1PI deficiency with endogenous plasma A1PI level of  $< 8 \mu\text{M}$  and documented A1PI genotypes of Pi\*Z/Z, Pi\*Z/null, Pi\*Malton/Z, Pi\*Null/Null, or other rare genotypes (except PI\*MS, PI\*MZ, or PI\*SZ). Intravenous (IV) ARALAST NP and GLASSIA augmentation therapy administered as an IV infusion at 60 mg/kg body weight (BW)/week or 120 mg/kg BW/week was to be compared to placebo. The protective effects of ARALAST NP and GLASSIA were expected to be reflected in the preservation of lung parenchyma, as measured by computerized tomography (CT) lung densitometry. In addition, the functional integrity of lung parenchyma was to be evaluated by measurements of selected respiratory physiology variables.

ARALAST NP and GLASSIA were approved by the Food and Drug Administration (FDA) for chronic augmentation and maintenance therapy in adults with clinically evident emphysema due to severe congenital deficiency of A1PI. The results of this study, along with available scientific data, may be used to design an adequately powered Stage 2 clinical study.

On 24 JUL 2018, Shire prematurely terminated the entire study following the unanimous vote by the Data Monitoring Committee (DMC) on 25 June 2018. The decision was based on the very low number of randomizations, slow rate of enrolling participants relative to the enrollment targets, and the difficulties of enrolling patients who would have to agree to be potentially randomized to receive placebo. Continuation of the trial would potentially place participants at increased risk due to the study procedures (including but not limited to radiation from the chest CT scan), not receiving active drug and inconvenience of study visits.

This statistical analysis plan (SAP) is based on Protocol Amendment 11 dated 21 JUN 2016 and provides a technical and detailed elaboration of the statistical analyses of efficacy and safety. Shells for tables, figures, and listings are contained in a separate document. Derivations of outcome variables, statistical analyses and summaries detailed in Protocol Amendment 11 which are no longer applicable are not included in this SAP. The summary tables that will be produced are for the disposition, demographic, exposure to investigational product (IP), and overall adverse event (AE) data. The data collected on the electronic case report form (eCRF) will be included in data listings. The listings will include raw (actual) values as recorded on the eCRF. In addition, since no adjudication of the response assessment data will be done, only the data based on the investigators' assessments will be presented in the listings.

## 2. OBJECTIVES, ESTIMAND(S), AND ENDPOINTS

### 2.1 Objectives

#### 2.1.1 Primary Objective

To evaluate the effect of weekly A1PI augmentation therapy on the rate of change in lung density assessed by CT lung densitometry, based on pooled data across dose levels for each of the A1PI products.

#### 2.1.2 Secondary Objectives

##### 2.1.2.1 Efficacy

To examine the relationship between A1PI dose (60 mg/kg BW/week and 120 mg/kg BW/week) and the rate of change in lung density assessed by CT densitometry for each of the A1PI products.

##### 2.1.2.2 Safety

- To assess the safety and tolerability of ARALAST NP and GLASSIA augmentation therapy at doses of 60 and 120 mg/kg BW/week.
- To monitor the formation of anti-A1PI antibodies following treatment with ARALAST NP or GLASSIA.

##### 2.1.2.3 Pharmacokinetics

To examine the relationship between A1PI dose and steady-state trough plasma A1PI levels following weekly administration of ARALAST NP or GLASSIA.

#### 2.1.3 Exploratory Objective(s)

█ [REDACTED]

█ [REDACTED]

█ [REDACTED]

█ [REDACTED]

[REDACTED]

## 2.2 Estimands

A specific description of estimands is not included in the protocol. Given that the study has been terminated early and no efficacy analyses will be provided, estimands have not been further defined for inclusion in this SAP.

## 2.3 Endpoints

The endpoints provided are from the protocol amendment 11. However, due to the study being prematurely terminated, the derived endpoints will not be presented in the data listing and analysis will not be performed using the endpoints.

### 2.3.1 Primary Endpoint

Rate of change in lung density (15th percentile of the lung density measurements [PD15] as assessed by CT densitometry), based on Group 1 and Group 2 (ARALAST NP) versus placebo, and Group 3 and Group 4 (GLASSIA) versus placebo

### 2.3.2 Secondary Endpoint

Rate of change in lung density (as assessed by CT) for each treatment group

### 2.3.3 Exploratory Endpoints

[REDACTED]

[REDACTED]

[REDACTED]

[REDACTED]

[REDACTED]

[REDACTED]

[REDACTED]

[REDACTED]

[REDACTED]

[REDACTED]

### 2.3.4 Safety Endpoints

1. Number and rate of related and unrelated serious and non-serious AEs
2. Number and rate of temporally related serious and non-serious AEs (ie, AEs which began during or within 72 hours following the end of IP infusion)
3. Number and rate of suspected adverse reactions plus adverse reactions
4. Number (proportion) of infusions for which the infusion rate was reduced and/or the infusion interrupted or stopped due to AEs
5. Number (proportion) of subjects who develop anti-A1PI antibodies following treatment with ARALAST NP or GLASSIA

### 2.3.5 Pharmacokinetic Endpoints

[figure not shown]
Mean steady state trough concentration of antigenic and functional A1PI for ARALAST NP and GLASSIA at each dose level.

## 3. STUDY DESIGN

### 3.1 General Description

This is a Phase 3/4, prospective, randomized, placebo-controlled, double-blind, multicenter pilot study to evaluate the safety and efficacy of weekly administration of ARALAST NP and GLASSIA augmentation therapy in subjects with A1PI deficiency and emphysema/COPD using a dose of 60 mg/kg BW/week (dose currently-approved by the FDA), and a higher, exploratory dose (120 mg/kg BW/week) versus placebo. The flow chart of the study follows:

### 3.1.1 Figure Study Flow Chart

Approximately 138 adult subjects diagnosed with severe congenital A1PI deficiency and emphysema/COPD were to be enrolled to meet the target of 110 randomized subjects, assuming a 20% screen failure rate. Subjects could be either A1PI naïve (untreated), previously treated, or currently receiving A1PI augmentation therapy at the time of study entry.

Subjects who were receiving or had been treated within 4 weeks of screening, with A1PI augmentation therapy would be required to have their pre-study A1PI augmentation therapy discontinued and undergo a washout period of at least 4 weeks for A1PI levels to return to endogenous (pre-augmentation) levels. Plasma A1PI levels were to be assessed to verify adequacy of A1PI washout and to confirm diagnosis of A1PI deficiency. All other screening procedures were to be performed prior to the completion of the washout period.

Subjects meeting eligibility criteria will undergo baseline assessments prior to the first dose of IP. Subjects were to be randomly assigned to receive one of the five treatments groups for 24 months (104 weeks). The IP was to be administered via weekly IV infusions. The first IP infusion was to be administered at the study site. At the investigator's discretion, subsequent infusions could be administered at the study site or at another suitable location (ie, the subject's home) by a qualified healthcare professional, except for those that occurred during the same week as the clinic visits.

Study visits occurred according to the schedule of events for clinical and laboratory assessments (see Appendix 15). Clinical and/or laboratory assessments, as appropriate, were to be postponed in the event of a moderate or severe lower respiratory tract infection (LRTI)/acute pulmonary exacerbation (APE) until clinical resolution of the LRTI/APE (ie, clinical signs or symptoms were no longer evident) and the subject remained stable for at least 4 weeks (or 90 days in the case of CT assessments) after the end of the LRTI/APE. If a moderate or severe episode of LRTI/APE occurred during the treatment phase, the subject should continue with the planned study visits and receive weekly infusions of IP as planned, unless deemed medically inappropriate by the investigator. All pulmonary exacerbations, AEs, and concomitant medications and/or non-drug therapies were to be recorded during infusion visits. Upon completion of the treatment period, subjects were to be followed for an additional 1 week ( $\pm$  2 days) for safety monitoring and anti-A1PI antibody assessments.

### **3.2 Randomization**

Subjects who meet all the inclusion criteria and none of the exclusion criteria will be randomized using the interactive voice response system (IVRS) at a ratio of 1:1:1:1:1.5 to receive one of the following five treatments for 24 months (104 weeks):

Group 1: ARALAST NP 60 mg/kg BW/week (20 subjects)

Group 2: ARALAST NP 120 mg/kg BW/week (20 subjects)

Group 3: GLASSIA 60 mg/kg BW/week (20 subjects)

Group 4: GLASSIA 120 mg/kg BW/week (20 subjects)

Group 5: Placebo (Human albumin 2% in normal saline) 6 mL/kg BW/week (30 subjects).

### **3.3 Blinding**

To maintain blinding, all subjects were to receive IP in 2 identical IV bags that were opaque or covered with opaque overwraps. Subjects in Group 1 and Group 3 were to receive 1 IV bag of active IP and 1 IV bag of volume-matched placebo solution (human albumin 2% in normal saline). Subjects in Group 2 and Group 4 were to receive two identical IV bags of active IP. Subjects in Group 5 were to receive two identical IV bags of placebo solution (human albumin 2% in normal saline). Treatment assignment will be blinded to the subject, investigators, study site personnel and the sponsor. Individual study personnel could be unblinded if necessary (e.g. to prepare the infusions or monitor the study source documents).

The randomization assignment is not to be revealed before the study is terminated, except in emergency cases when unblinding is necessary for the clinical management of an SAE. In such events, every attempt must be made to inform the sponsor before breaking the blind or immediately when unblinding has been performed. The investigator may request for the treatment assignment of the specific individual subject involved in the emergency event via the centralized randomization service or the unblinded biostatistician.

### **3.4 Sample Size and Power Considerations**

The sample size proposed for this study will permit estimates of averages and variances in the rate of change of lung density and other parameters after 24 months of treatment in each treatment group and pooled within product. This study will not be powered to permit hypothesis tests of primary or secondary outcome measures.

## **4. STATISTICAL ANALYSIS SETS**

### **4.1 Screened Set**

The Screened Set will consist of all subjects who have signed informed consent.

### **4.2 Enrolled Set**

Enrolled Set consists of all subjects who have signed informed consent and passed inclusion/exclusion criteria.

### **4.3 Intent-to-Treat Set**

Intent-to-Treat (ITT) Set consists of all subjects in the Enrolled Set who have been allocated to a treatment regimen. Analysis will be performed according to allocated treatment regimen regardless of the treatment regimen received.

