### **4.4 Safety Set**

The Safety Set will consist of all subjects who receive any amount of IP, regardless of protocol deviations or non-adherence to study procedures. Analysis will be performed according to the treatment regimen received regardless of the randomized treatment regimen.

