## **5. STUDY SUBJECTS**

### **5.1 Disposition of Subjects**

A listing of all Screen Failures (i.e., subjects who were screened, but not included in the Enrolled Set) will be presented. Any AEs related to Screen Failures will be provided in the AE data listings.

The number of subjects who were included in and excluded from each defined analysis set (i.e., Screened, Enrolled, ITT, and Safety) will be summarized by treatment group, and overall; except for the Screened Set and Enrolled, which will be summarized only overall.

The number and percentage of subjects who completed and prematurely discontinued during the double-blind evaluation phase will be presented for each treatment group and overall for ITT Set. Reasons for premature discontinuation from the double-blind evaluation phase as recorded on the termination page of the electronic Case Report Form will be summarized (number and percentage) by treatment group and overall for the Safety Set. All subjects who prematurely discontinued during the double-blind evaluation phase will be listed by discontinuation reason for Enrolled Set.

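### ITT membership depends on passing the eligibility criteria, so a subject randomised despite failing one falls outside ITT and becomes a Screen Failure, even if dosed

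*SAP*

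**What the plan says.** Four definitions in the SAP bear on this point, together with the uses made of them in Section 5.1.

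- Section 4.2: "Enrolled Set consists of all subjects who have signed informed consent and passed inclusion/exclusion criteria".
- Section 4.3: "Intent-to-Treat (ITT) Set consists of all subjects in the Enrolled Set who have been allocated to a treatment regimen". The rule that follows is the usual as-randomised one: "Analysis will be performed according to allocated treatment regimen regardless of the treatment regimen received".
- Section 4.4: "The Safety Set will consist of all subjects who receive any amount of IP, regardless of protocol deviations or non-adherence to study procedures".
- Section 5.1 defines Screen Failures as "subjects who were screened, but not included in the Enrolled Set".

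Section 5.1 then uses three different sets for one account of disposition. Completed and discontinued counts are on the ITT Set. Reasons for discontinuation are on the Safety Set. The listing is on the Enrolled Set: "All subjects who prematurely discontinued during the double-blind evaluation phase will be listed by discontinuation reason for Enrolled Set". Section 5.6 lists protocol deviations for the Safety Set.

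**The concern.** An ITT set should contain everyone allocated, whatever is later found about eligibility. Here the as-allocated analysis rule is present, but membership is filtered through the Enrolled Set, which carries an eligibility condition. The Safety Set explicitly tolerates protocol deviations; the Enrolled and ITT Sets do not.

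Disposition is one of the four summary topics that the SAP keeps (Sections 1 and 12). A subject randomised in breach of a criterion, such as the A1PI level or genotype named in Section 1, would be missing from the ITT counts and from the discontinuation listing, and would be listed as a Screen Failure. If dosed, the same person would also be in the demographic, exposure and adverse event tables. The number randomised and the number discontinued could each be too low, and the number of screen failures too high.

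**Working it through.** **The plan's own figure.** Section 3.1.1 gives 110 / (1 − 0.20) = 137.5, rounded up to 138 to be enrolled for 110 randomised. This reproduces, and nothing here depends on it. It does show that the word enrolled is used in two ways. In Section 3.1.1 the 138 enrolled include the expected 138 − 110 = 28 screen failures. In Sections 4.2 and 5.1 nobody can be both enrolled and a Screen Failure.

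**Set logic under the current text.** All subjects are screened. Enrolled = passed; ITT = Enrolled and allocated; Safety = dosed; Screen Failure = not Enrolled.

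| Criteria | Randomised | Dosed | Enrolled | ITT | Safety | Screen Failure |
|---|---|---|---|---|---|---|
| passed | yes | yes | 1 | 1 | 1 | 0 |
| passed | yes | no | 1 | 1 | 0 | 0 |
| passed | no | no | 1 | 0 | 0 | 0 |
| failed | yes | yes | 0 | 0 | 1 | 1 |
| failed | yes | no | 0 | 0 | 0 | 1 |
| failed | no | no | 0 | 0 | 0 | 1 |

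The fourth row is the contradiction: a treated subject who is also a Screen Failure, so that the Safety Set is not contained in ITT. The fifth row is a randomised subject who appears only as a Screen Failure and, never having been dosed, is not in the deviation listing either.

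**Where a randomised subject who discontinues would appear.** Each cell gives current text → after the three sets are redefined as proposed below.

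| Subject | Count (ITT) | Reason (Safety) | Listing (Enrolled) | Screen Failure |
|---|---|---|---|---|
| failed, dosed | 0 → 1 | 1 → 1 | 0 → 1 | 1 → 0 |
| failed, not dosed | 0 → 1 | 0 → 0 | 0 → 1 | 1 → 0 |
| passed, not dosed | 1 → 1 | 0 → 0 | 1 → 1 | 0 → 0 |

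Redefining the sets settles the first row. In the other two, the subject still has a discontinuation count of 1 and no reason, because counts use ITT and reasons use Safety. That disagreement needs no ineligible subject, so it is a separate matter with its own remedy.

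**Size per subject.** Each affected subject lowers the Enrolled and ITT counts by 1 and raises Screen Failures by 1. The SAP does not give the number randomised; Section 1 calls it very low. Assuming 10 to 30, one subject is 1/10 = 10% down to 1/30 = 3.3% of those randomised.

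**The case against.** The best reply is that *passed* means cleared at screening. Table 14-1 schedules the eligibility determination once, at screening; Section 3.2 makes randomisation follow from it; and a Screen Failure is by its nature a screening outcome. On that reading, a subject who cleared screening, was infused and was only then found ineligible stays in the Enrolled and ITT Sets. A reader might infer that every subject later found ineligible is removed from ITT. The documents do not support that without settling what *passed* means, and Section 4.2 does not. What remains on this reading is narrower: a subject randomised despite a failure already recorded at screening. Section 3.2 says who should be randomised and gives no rule for errors.

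A reader might also infer that the report will misstate its counts. No such subject is documented, so the effect is conditional. Nor should cotinine serve as an example of a failed criterion: the SAP lists it only as a laboratory test.

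Finally, little rests on ITT here. A reader might expect the usual harm of excluding randomised subjects, a biased treatment comparison. It cannot arise, because Sections 2.2 and 6 remove all efficacy analysis. Demographics, exposure and the adverse event summary use the Safety Set and keep any dosed subject. Section 5.1 also tabulates inclusion in each set, so a Safety count above ITT could be noticed. These points limit the size of the defect; they do not remove it.

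**Conclusion.** The point holds as a defect in the definitions. As written, a subject randomised despite failing a criterion is outside the Enrolled and ITT Sets and is a Screen Failure, even when dosed. If *passed* means cleared at screening, this reaches only subjects randomised despite a failure recorded at screening; if it means actually met, it also reaches those found ineligible later.

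The consequence is limited to the set counts, the completed and discontinued counts, the discontinuation listing and the Screen Failure listing. It is one subject per case, or 3.3% to 10% of those randomised under the assumed 10 to 30, and nothing if no such subject exists. The correction is worth making because it is standard and cheap, and because two programmers could now derive different flags from the same text.

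**What to change.** 1. Section 4.3: define the ITT Set as all subjects allocated to a treatment regimen, analysed as allocated, regardless of eligibility.
2. Section 4.2: define the Enrolled Set so that it contains every randomised subject, for example consented and either cleared by the site at screening or randomised.
3. Section 5.1: define a Screen Failure as screened, not randomised and not dosed.
4. Separately, in Section 5.1, present discontinuation counts and reasons on the same set, ITT.
5. Section 5.6: run the deviation listing on a set that includes randomised undosed subjects, so that eligibility breaches are reported there and not through set membership.

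The cost is wording in Sections 4.2, 4.3, 5.1 and 5.6, revised flag derivations, and a change of set for one table and one listing. No new data are needed, and no sample-size figure changes.

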### **4.4 Safety Set**

The Safety Set will consist of all subjects who receive any amount of IP, regardless of protocol deviations or non-adherence to study procedures. Analysis will be performed according to the treatment regimen received regardless of the randomized treatment regimen.

## **5. STUDY SUBJECTS**

### **5.1 Disposition of Subjects**

A listing of all Screen Failures (i.e., subjects who were screened, but not included in the Enrolled Set) will be presented. Any AEs related to Screen Failures will be provided in the AE data listings.

The number of subjects who were included in and excluded from each defined analysis set (i.e., Screened, Enrolled, ITT, and Safety) will be summarized by treatment group, and overall; except for the Screened Set and Enrolled, which will be summarized only overall.

The number and percentage of subjects who completed and prematurely discontinued during the double-blind evaluation phase will be presented for each treatment group and overall for ITT Set. Reasons for premature discontinuation from the double-blind evaluation phase as recorded on the termination page of the electronic Case Report Form will be summarized (number and percentage) by treatment group and overall for the Safety Set. All subjects who prematurely discontinued during the double-blind evaluation phase will be listed by discontinuation reason for Enrolled Set.

### **5.2 Demographic and Other Characteristics at Screening**

Descriptive summaries of demographic and characteristics at screening will be presented by treatment group and overall for the Safety Set.

The following demographic characteristics will be summarized in the following order in the tables: age (years), sex, ethnicity, race, weight (kg), height (cm), body mass index (BMI) (kg/m^2), and smoking history. Age is calculated as the date of consent minus the

date of birth. Descriptive statistics (n, mean, standard deviation, minimum, median, and maximum) will be presented by treatment group and overall for continuous variables. The number and proportion of subjects will be presented by treatment group and overall for categorical variables. A listing of the data will be provided using the Safety Set.

### **5.3 Medical History**

Medical history will be collected at the Screening Visit (Visit 1) and will be coded using the Medical Dictionary for Regulatory Activities (MedDRA) Version 21.0 or newer. A listing of the data will be provided using the Safety Set.

### **5.4 Concomitant Medications, Non-Drug Therapy, and Procedures**

Concomitant medications will be coded using the WHO Drug Dictionary dated 01Mar2018. Concomitant non-drug therapies and procedures will be coded using MedDRA Version 21.0 or newer.

All concomitant medications, non-drug therapies, and procedures will be listed for the Safety Set.

### **5.5 Exposure to Investigational Product**

Exposure to IP for the Safety Set will be summarized in terms of number of infusions, duration of exposure, and average weekly dose. The duration of exposure is calculated as the number of days from the date of first dose of IP taken to the date of the last dose of IP taken, inclusively. The average weekly dose is calculated as (total volume administered/ total planned volume) \* actual dose (either 60 mg or 120 mg). For placebo, the actual dose would be 0. The average weekly dose is the average of the weekly doses for each subject.

Descriptive statistics (n, mean, standard deviation, minimum, median, and maximum) will be presented to describe the exposure to IP by treatment group and overall.

The number and proportion of subjects with at least one infusion rate change, one infusion rate interruption, or one infusion stopped will be summarized by treatment and overall.

The details of exposure to IP will be listed for the Safety Set.

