## 7.1 Adverse Events

Adverse events will be coded using MedDRA Version 21.0 or newer.

An AE (classified by preferred term) that occurs during the double-blind evaluation phase will be considered a treatment-emergent AE (TEAE) if it has a start date on or after the first dose of double-blind IP or if it has a start date before the date of the first dose of double-blind IP, but increases in severity on or after the date of the first dose of double-blind IP.

An overall summary of the number of subjects with TEAEs as well as the number of events by treatment group and overall will be presented. The table will also be summarized by any TEAEs during or within 72 hours following the end of the IP infusion. The table will include the number and percentage of subjects with any TEAEs, serious TEAEs, severe TEAEs, TEAEs related to IP and TEAEs leading to discontinuation of IP.

All AEs will be listed for the Safety Set.

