## 12. CHANGES TO ANALYSIS SPECIFIED IN PROTOCOL

As indicated in Section 1, Shire prematurely terminated the entire study on 24 July 2018 following the unanimous vote by the DMC on 25 June 2018. The decision was based on the very low number of randomizations, slow rate of enrolling participants relative to the enrollment targets, and the difficulties of enrolling patient who would have to agree to be potentially randomized to receive placebo. Continuation of the trial would potentially place participants at increased risk due to the study procedures (including but not limited to radiation from the chest CT scan), not receiving active drug and inconvenience of study visits.

This SAP includes the analyses that will be provided for the abbreviated study report. The derivations, statistical analyses and summaries of the study endpoints (See Section 2.3) noted in Protocol Amendment 11 are no longer applicable. The only summary tables that will be produced are for the disposition, demographic, exposure to IP, and overall AE data. A full set of data listings will be produced. The listings will include raw (actual) values. In addition, since no adjudication of the response assessment data will be done, only the data based on the investigators' assessments will be presented in the listings. The Full Analysis, Modified Full Analysis, and Per-Protocol Sets will not be defined because the populations will not be needed to list the data. The listings will be presented for the largest meaningful analysis set (e.g., Enrolled Set or Safety Set), depending on the content.

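### Does the subject-level infusion-modification summary in SAP Section 5.5 misreport the safety endpoint on infusions modified because of AEs?

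*SAP*

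**What the plan says.** Section 2.3.4 carries over five safety endpoints from Protocol Amendment 11. The fourth is "Number (proportion) of infusions for which the infusion rate was reduced and/or the infusion interrupted or stopped due to AEs". The introduction to Section 2.3 states their status after the premature termination: "the derived endpoints will not be presented in the data listing and analysis will not be performed using the endpoints". Section 12 repeats this as a declared change from the protocol: "The derivations, statistical analyses and summaries of the study endpoints (See Section 2.3) noted in Protocol Amendment 11 are no longer applicable". It then limits the tabulated output: "The only summary tables that will be produced are for the disposition, demographic, exposure to IP, and overall AE data".

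Section 5.5 belongs to the chapter on study subjects, not to the safety chapter (Section 7). It opens with "Exposure to IP for the Safety Set will be summarized in terms of number of infusions, duration of exposure, and average weekly dose". For each treatment group and for all groups together it adds the subject-level summary "The number and proportion of subjects with at least one infusion rate change, one infusion rate interruption, or one infusion stopped will be summarized", and it closes with "The details of exposure to IP will be listed for the Safety Set".

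Section 7.1 plans an overall TEAE table with subject and event counts, including IP-related TEAEs and TEAEs leading to discontinuation of IP. On timing it says "The table will also be summarized by any TEAEs during or within 72 hours following the end of the IP infusion". All AEs are also listed. Section 1 says that the shells for tables and listings are kept in a separate document.

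**The concern.** Section 5.5 gives the only planned summary of infusion modification, and it differs from the fourth safety endpoint in unit, event and cause. It also does not say whether rate increases count, or whether rate changes, interruptions and stops are shown separately or combined. A proportion of subjects with at least one event rises with the number of infusions received, and early termination probably makes that number uneven between subjects.

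If a reader took this summary as the tolerability result, a harmless upward rate change could look like an AE-driven reduction, and one subject with many interruptions would count the same as one subject with a single interruption. The descriptive safety picture for each product and dose could then mislead.

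**Working it through.** The SAP gives no figure for this point, so there is none to reproduce. The check has two parts: a comparison of the texts, and an illustration of how far the two measures can differ.

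**1. The two measures side by side**

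| | Section 2.3.4, item 4 | Section 5.5 summary |
|---|---|---|
| Unit | infusions | subjects |
| Event | rate reduced, infusion interrupted or stopped | rate change, interruption or stop |
| Cause | AEs only | none stated |
| Status in this SAP | not analysed (Sections 2.3 and 12) | retained as an exposure table (Section 12) |

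The first three rows confirm that the measures differ. The last row decides the matter: the SAP has withdrawn the endpoint, and Section 5.5 does not refer to it.

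**2. How far the measures can differ (assumed inputs)**

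Assume 5 subjects with 52 infusions each, so 5 × 52 = 260 infusions in a group. The SAP gives neither number.

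- Case A: each subject has one upward rate change and no AE. Subjects with any modification: 5/5 = 100%. AE-driven infusions: 0/260 = 0%.
- Case B: each subject has 10 AE-driven interruptions. Subjects: 5/5 = 100%. Infusions: 50/260 = 19.2%.
- Case C: one subject has 30 AE-driven interruptions. Subjects: 1/5 = 20%. Infusions: 30/260 = 11.5%.
- Case D: each of five subjects has one AE-driven interruption. Subjects: 5/5 = 100%. Infusions: 5/260 = 1.9%.

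Cases A and B look alike only if the three kinds of event are merged into one count. With separate rows, Case A shows rate change 5/5 and interruption 0/5, while Case B shows rate change 0/5 and interruption 5/5. The SAP text does not settle the layout, so this contrast cannot be charged against it. Cases B and D still look alike with separate rows, and C against D still reverses the order. They show that a subject count is not an infusion proportion, which is true of any such pair of measures.

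**3. Dependence on exposure (assumed inputs)**

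With independent infusions and a per-infusion risk p, the chance of at least one event in m infusions is 1 − (1 − p)^m. At p = 2%:

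- m = 13: 1 − 0.98^13 = 23.1%
- m = 52: 1 − 0.98^52 = 65.0%
- m = 67: 1 − 0.98^67 = 74.2%
- m = 104 (the full planned course of weekly infusions): 1 − 0.98^104 = 87.8%

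Comparing groups that average 52 and 67 infusions, the gap is 74.2 − 65.0 = 9.2 points. In a group of five that is 0.092 × 5 = 0.46, under half a subject. The same dependence affects every subject-level incidence, including the TEAE percentages in Section 7.1. Because Section 5.5 summarises number of infusions and duration by group, a reader can see any imbalance.

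**The case for a change.** The strongest case against this reading is that the SAP chose to keep an infusion-modification summary by treatment, and having kept it should define it so that it can be interpreted. The SAP also keeps summaries close to other safety endpoints: the 72-hour TEAE summary in Section 7.1 and, if data are available, the antibody counts in Section 7.5. A reader might therefore take the Section 5.5 row for the fourth endpoint. No planned table described in the SAP supplies the numerator of that endpoint, since the AE table covers discontinuation of IP but not reductions or interruptions. Rebuilding it from listings means going through up to 104 infusions per subject, and works only if cause was recorded.

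Part of this stands. The measures do differ, and the SAP text leaves open the row layout and the meaning of a rate change. But keeping output near two endpoints does not reinstate a third that has been expressly withdrawn. That increases count, or that every cause counts, is inferred from silence in the SAP, and the shells that could settle either point are not at hand. With very few subjects randomised, listings are a reasonable vehicle for detail of this kind.

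Setting TEAE counts beside infusions or subject-time would be a convenience. Section 7.1 already plans event counts and Section 5.5 already summarises infusions and duration, so a reader can work out a rate, which would be imprecise in groups this small.

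**Conclusion.** The concern does not hold. The difference in wording between Sections 5.5 and 2.3.4 is real, but the comparison uses a benchmark that Sections 2.3 and 12 openly set aside. As an exposure description, the subject count is correct for what it says it counts, and nothing else in the SAP contradicts it. Reporting AE-driven modifications per infusion would restore a dropped analysis, which is a matter of preference in an abbreviated descriptive report without between-group inference.

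The possible gap between the measures is wide in the illustrations (5/5 subjects with 1.9% or 19.2% of infusions), but every input there apart from the 104 planned infusions is assumed. The conclusion rests on reading Section 5.5 as an exposure table only. It would change if the shells or the report presented that row as the result for the fourth safety endpoint, and nothing in the SAP indicates this.
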